## 2.0 LIST OF ABBREVIATIONS

| Abbreviation or Term | Definition                                   |
|----------------------|--|
| AE                   | adverse event                                |
| BL                   | Baseline                                     |
| CKD                  | chronic kidney disease                       |
| CONSORT              | Consolidated Standards of Reporting Trials   |
| CRO                  | contract research organization               |
| DD                   | dialysis-dependent                           |
| eCRF                 | electronic case report form                  |
| EDC                  | electronic data capture                      |
| eGFR                 | estimated glomerular filtration rate         |
| EOT                  | end of treatment                             |
| ESA                  | erythropoiesis-stimulating agent             |
| ET                   | early termination                            |
| FDA                  | (United States) Food and Drug Administration |
| GCP                  | Good Clinical Practice                       |
| GI                   | Gastrointestinal                             |
| GLP                  | Good Laboratory Practice                     |
| GMP                  | Good Manufacturing Practice                  |
| Hb                   | Hemoglobin                                   |
| HR                   | hazard ratio                                 |
| ICF                  | informed consent form                        |
| ICH                  | International Council for Harmonisation      |
| IDA                  | iron deficiency anemia                       |
| IEC                  | Independent Ethics Committee                 |
| IRB                  | Institutional Review Board                   |
| IV                   | Intravenous                                  |
| KDIGO                | Kidney Disease: Improving Global Outcomes    |
| KFRE                 | Kidney Failure Risk Equation                 |
| MedDRA               | Medical Dictionary for Regulatory Activities |
| NDD                  | non-dialysis-dependent                       |
| RBC                  | Red Blood Cell                               |

USRC Kidney Research  
Original Version 5.0  
28JUL2022  
Protocol No USRC-2021-002

| Abbreviation or Term | Definition                       |
|----------------------|----------------------------------|
| PP                   | per protocol                     |
| QC                   | quality control                  |
| SAE                  | serious adverse event            |
| SoA                  | Schedule of Activities           |
| SOC                  | standard of care                 |
| TEAE                 | treatment-emergent adverse event |
| TSAT                 | transferrin saturation           |
| US                   | United States                    |
| USRDS                | United States Renal Data System  |

### **3.0 INTRODUCTION**

This is a multicenter, randomized, double-blind, placebo-controlled clinical trial to determine the effect of ferric citrate on time to a composite endpoint of initiation of maintenance dialysis or all-cause mortality compared to placebo in adult patients with advanced chronic kidney disease (CKD). This study is funded by Akebia Therapeutics, Inc.

#### **3.1 Study Rationale**

Ferric citrate is an iron-based phosphate binder and has been extensively studied for the treatment of hyperphosphatemia in subjects with dialysis-dependent chronic kidney disease (DD-CKD) and for the treatment of iron deficiency anemia (IDA) in subjects with non-dialysis-dependent chronic kidney disease (NDD-CKD). Epidemiological evidence suggests that patients with CKD are at greater risk of adverse outcomes due to higher incidence of anemia in this population. The severity of anemia is directly related to the occurrence of cardiovascular events in this patient population. A pilot randomized trial of ferric citrate compared to standard of care in 200 subjects with advanced CKD showed that subjects treated with ferric citrate demonstrated significant changes in laboratory values associated with improvements in anemia and iron. Additionally, this pilot study demonstrated a clinically significant reduction in the risk of the composite endpoint of death, dialysis, or transplantation in patients randomized to ferric citrate. [Block 2019]. It has been recommended by a KDIGO Conference Report that there is a priority need to study the effects of iron repletion in those without overt anemia. This study is being conducted in a population of patients chosen purposefully to reflect the broad characteristics of individuals with advanced CKD and is not restricted only to those with iron deficiency nor hyperphosphatemia.

This study is being conducted to determine if ferric citrate will delay the progression of advanced CKD to kidney failure requiring maintenance dialysis or death, compared to placebo in adult patients with advanced CKD.

#### **3.2 Background**

##### **3.2.1 Iron Deficiency Anemia**

CKD affects up to 14.9% of adults in the United States (US) [USRDS 2020] and markedly increases the risk of premature cardiovascular events [McCullough 2021, Foley 2005]. Anemia is a common complication of CKD, and is associated with mortality and cardiovascular events, even after accounting for CKD stage and other cardiovascular risk factors, including albuminuria, diabetes mellitus, smoking, and hypercholesterolemia [Kovesdy 2006].

International clinical practice guidelines for anemia in CKD by the Kidney Disease: Improving Global Outcomes (KDIGO) 2012 anemia work group recommend evaluation for and resolution of correctable causes of anemia in subjects with CKD and anemia [KDIGO 2012]. While the anemia of CKD is multifactorial in origin, 60% to 73% of persons with estimated glomerular filtration rate (eGFR)  $<60$  mL/min/1.73 m^2 are iron-deficient [Fishbane 2009]. Therefore, in persons with CKD and anemia (hemoglobin [Hb]  $<13$  g/dL for men;  $<12$  g/dL for women), the

guidelines suggest a trial of iron to increase the Hb if transferrin saturation (TSAT) is  $\leq 30\%$  and serum ferritin is  $\leq 500$  ng/mL.

The goals of iron therapy are to avoid iron storage depletion, to prevent impairment of erythropoiesis due to iron deficiency, and to help achieve and maintain target Hb levels. When prescribing iron therapy, the guidelines recommend to “balance the potential benefits of avoiding or minimizing blood transfusions, erythropoiesis-stimulating agent (ESA) therapy, and anemia-related symptoms against the risks of harm in individual subjects (e.g., anaphylactoid and other acute reactions, unknown long-term risks)” [Van Wyck 2000, KDIGO 2012].

For CKD patients on dialysis, iron is usually given intravenously, but oral iron is preferred in patients with NDD-CKD for its convenience and low cost. However, the tolerability and efficacy of currently available oral iron formulations is often limited by gastrointestinal (GI) side effects, poor adherence to therapy, and poor absorption [Drueke 2012; Cancelo-Hidalgo 2013; Macdougall 2016]. IV iron use remains low in persons with NDD-CKD [Wetmore 2015]. Anaphylactoid and other acute reactions are infrequent but potentially life-threatening complications of IV iron treatment [Wang 2015]. These risks have resulted in black box warnings, or Warnings and Precautions. IV iron administration requires additional safety measures for administration, resulting in higher personnel costs and more time required for these therapies. The long-term safety of IV iron administration has also not been established, and there are concerns that patients may be exposed to increased oxidative stress and greater vulnerability to infections [Macdougall 2016]. Further, IV iron administration can be burdensome for patients, requiring visits to clinics or infusion centers.

ESAs are another treatment modality for anemia of CKD that are widely used in DD-CKD patients but safety concerns due to excess cardiovascular risk for ESAs resulted in black box warnings in 2007.

### **3.2.2      Hyperphosphatemia**

In healthy individuals, phosphate is primarily eliminated by the kidneys, which effectively regulate phosphate balance and blood phosphate concentration. With decreasing kidney function, and other changes associated with CKD, there is a marked decrease in phosphorus excretion in the urine, leading to hyperphosphatemia. Hyperphosphatemia contributes to bone disease, vascular calcification, cardiovascular events, and mortality [Martin and Gonzalez 2011].

Restriction of dietary phosphate is usually not sufficient to control hyperphosphatemia in patients with DD-CKD; therefore, these patients are treated with orally administered phosphate binders which effectively bind dietary phosphate and facilitate fecal elimination rather than intestinal absorption. However, different phosphate binders differ in their safety profile, and all pose a high pill burden [Salusky 2006]. Specific safety or cost concerns with existing phosphate binders resulted in a persistent high level of unmet need for patients with hyperphosphatemia, which resulted in the development of ferric citrate as a phosphate binder in patients with DD-CKD.

Ferric citrate reduces intestinal phosphate absorption by precipitating phosphate in the intestine. The ferric iron from ferric citrate reacts with the phosphorus in the GI tract and precipitates as ferric phosphate or ferrous phosphate. The latter are insoluble and are excreted in the stool. Citrate is absorbed, potentially alleviating the metabolic acidosis that occurs in patients with

renal failure. Ferric citrate is approved for the control of serum phosphorus levels in adult patients with CKD on dialysis.

### **3.3 Risk/Benefit Assessment**

#### **3.3.1 Known Potential Risks**

A thorough summary of the risks of ferric citrate is provided in the Investigator Brochure. (Edition 14, 10 March 2020). The main source of information on the safety of ferric citrate in humans comes from two main datasets. One dataset, the risks Pooled Safety Set – Hyperphosphatemia, is based on the integrated data from four completed studies (Studies 304, 305, PBB00101, and 201). These studies involved subjects with DD-CKD treated for hyperphosphatemia with ferric citrate for up to 1 year at dosages of up to 12 g/day. In these four studies, a total of 557 subjects received ferric citrate, 149 subjects received active control and 111 subjects received placebo.

The second dataset, the Pooled Safety Set – IDA, is based on the integrated data from 3 studies (Studies 306, 204, and 207). These studies involved 405 unique subjects (excluding 9 subjects treated in Study 204 and Study 306) with NDD-CKD IDA. In these 3 studies, 301 received ferric citrate (including 81 subjects treated with placebo in the Randomized Period and ferric citrate in the Extension Period of Study 306 and excluding 2 subjects treated with ferric citrate in Study 204 and Study 306) and 188 received placebo (excluding 1 subject treated with placebo in Study 204 and Study 306).

In the hyperphosphatemia pooled safety set, the incidence of subjects who experienced at least one treatment-emergent adverse event (TEAE) was lower in the all ferric citrate group (77.5%) compared with subjects on active control (89.3%). The most common TEAEs in subjects receiving ferric citrate were diarrhea (20.8%), discolored feces (19.4%), and nausea (11.1%). The most common TEAEs in subjects receiving active control were vomiting (14.8%), nausea (14.1%), diarrhea (14.1%), dyspnea (13.4%), vascular access complication (11.4%), hypotension (10.7%), and cough (10.1%).

In the IDA pooled safety set in the randomized periods, the incidence of subjects who experienced at least 1 TEAE was higher among subjects who received ferric citrate (75.3%) than among subjects who received placebo (61.7%). The most common TEAEs in subjects receiving ferric citrate were discolored feces (21.6%), diarrhea (20.5%), constipation (18.4%), nausea (9.5%), hyperkalemia (5.3%), and abdominal pain (4.7%). The most common TEAEs in subjects receiving placebo were diarrhea (12.2%), constipation (10.1%), and nausea (4.3%).

Iron accumulation is a potential risk of long-term treatment with ferric citrate or other iron-containing medicinal products. Continued excessive iron uptake can lead to iron deposition in body tissues and ultimately to organ damage. To prevent excessive iron accumulation, laboratory iron measures will be monitored regularly, and the ferric citrate, oral or IV iron dose will be adjusted in response to sustained elevations of TSAT.

### **3.3.2 Known Potential Benefits**

The ability of ferric citrate to lower serum phosphorus in adult patients with CKD on dialysis was demonstrated in Study KRX-0502-304. In that pivotal study, the efficacy of ferric citrate for controlling serum phosphorus levels was similar to that of calcium acetate and/or sevelamer carbonate, and better than that of placebo.

Study KRX-0502-204 was a 12-week, double-blind, placebo-controlled study.

Study KRX-0502-306 was a 24-week study consisting of a 16-week, randomized, double-blind, placebo-controlled, efficacy period followed by an 8-week, open-label, safety extension period in which all subjects remaining in the study, including those in the placebo group, received ferric citrate. Both studies showed reduction in serum phosphorus levels with ferric citrate treatment compared with placebo. In addition, the efficacy of ferric citrate for the treatment of IDA was demonstrated in 2 controlled studies in adult subjects with CKD not on dialysis.

Ferric citrate's potential benefits are supported by its approval for use in the US for the control of serum phosphorus levels in adult patients with CKD on dialysis, and for the treatment of IDA in adult patients with CKD not on dialysis.

### **3.3.3 Overall Benefit: Risk Conclusion**

No significant change in the safety profile of ferric citrate has been identified in post-marketing surveillance. A recent study demonstrated that treatment with ferric citrate significantly improves anemia in subjects with advanced CKD without the routine use of supplemental iron or ESAs. The results of the study suggest that treatment with ferric citrate can improve clinical outcomes for these subjects, is safe, and potentially beneficial [Block 2019]. The risk-benefit profile of ferric citrate in the treatment of adult patients with CKD remains favorable in the commercial setting.

## **4.0 OBJECTIVES AND ENDPOINTS**

### **4.1 Study Objectives**

#### **4.1.1 Primary Objective**

To determine the effect of ferric citrate on the time to a composite endpoint of initiation of maintenance dialysis or all-cause mortality compared to placebo in adult patients with advanced CKD.

#### **4.1.2 Secondary Objective**

To evaluate the impact of ferric citrate on time to all-cause hospitalization and individual components of the primary endpoint.

## **4.2 Study Endpoints**

### **4.2.1 Primary Endpoint**

Time to a composite endpoint of initiation of maintenance dialysis or all-cause mortality

### **4.2.2 Secondary Endpoints**

Secondary endpoints include:

1. Time to first hospitalization event reported as a serious adverse event (SAE) (excluding disease-related hospitalization [e.g., dialysis access placement, dialysis initiation, kidney transplant] and elective procedures)
2. Component of Primary – Time to Initiation of Maintenance Dialysis
3. Component of Primary – Time to All-Cause Mortality

### **4.2.3 Exploratory Endpoints**

Exploratory endpoints include:

1. Annualized hospital days prior to initiating maintenance dialysis
2. Receipt of kidney transplant prior to initiating maintenance dialysis
3. Cumulative utilization of rescue therapy for anemia including (individually, [ESA, intravenous iron, RBC transfusion]) prior to initiating maintenance dialysis
4. Time to a composite of death, dialysis, or kidney transplant

## **5.0 STUDY DESIGN**

### **5.1 Overall Design**

This is an investigator-initiated multicenter, randomized, double-blind, placebo-controlled, pragmatic clinical trial in patients with advanced CKD to determine the effect of ferric citrate versus matching placebo on the time to a composite endpoint of maintenance dialysis or all-cause mortality.

Subjects who meet all inclusion and none of the exclusion criteria will be randomized in a 1:1 ratio (stratified by site and eGFR) to receive either ferric citrate or matching placebo. All subjects will receive a fixed dose of 2 tablets orally taken with meals or snacks up to 3 times per day. The maximum daily dose is 6 tablets/day. Subjects will remain on study drug for up to 9 months followed by an additional 30-day safety follow-up period. Study drug will be stopped for subjects who initiate maintenance dialysis or receive a kidney transplant. Subjects who undergo maintenance dialysis or receive a kidney transplant will be removed from study with no follow-up visit, however, these subjects will have a vital status check (to ascertain mortality) performed at 30-days following the relevant event.

The study periods are:

- Screening Period: Up to 45 days prior to Day 1. Standard of Care (SOC) laboratory collection permitted up to 45 days (up to 90 days for eGFR) prior to Day 1.
- Treatment Period: Up to 9 months
- Safety follow-up Period: 30 days after EOT

Each randomized subject will complete 5 study visits (2 in-person and 3 phone/virtual or in-person). In-person study visits should attempt to coincide with routine standard of care office visits and relevant clinical data from such standard of care visits (including assessments for possible endpoint events or adverse events) will be collected and entered into the electronic case report form (eCRF). Standard of care (SOC) laboratory assessments as ordered by the primary nephrologist will be utilized. Iron status and serum phosphate collection and monitoring will be required as part of the SOC laboratory assessments. Laboratory assessments captured in the eCRF other than a screening pregnancy test for women of child-bearing potential and non-SOC iron and serum phosphorus labs, will utilize local laboratory results.

Study drug is not intended to be used as a treatment for either serum phosphorus or iron repletion. Management of serum phosphorus and iron sufficiency will be directed at the discretion of the treating physician and/or Investigator independent of study drug with the exception of protocol required safety adjustments of study drug. The prescribed dose of study drug will be adjusted only in the event of a safety or tolerability concern (as described in Section 7.1.2.1). Investigators will be instructed not to prescribe commercial ferric citrate (Auryxia) to any study participant; however, all other phosphate lowering therapy or iron repletion therapy may be prescribed at the discretion of the PI according to local standard of care.

[figure not shown]
Subjects may or may not be prescribed phosphate-lowering or iron-repletion therapy prior to Day 1; however, if a subject is receiving commercial ferric citrate (Auryxia), it must be stopped at or prior to Day 1.

### **5.1.1 Replacement of Participants**

Subjects who sign the informed consent form (ICF) and are randomized but do not receive the study intervention may be replaced at the discretion of the Investigator or Investigator-Sponsor. Subjects who sign the ICF and are randomized, receive any dose of the study intervention, and then subsequently withdraw, or are withdrawn or discontinued from the study, will not be replaced.

### **5.2 Scientific Rationale for Study Design**

A pilot randomized trial of ferric citrate in patients with advanced CKD demonstrated that, as compared to standard of care therapy, patients randomized to ferric citrate showed a significant reduction in progression to maintenance dialysis ( $p=0.001$ ) as well as a significantly lower incidence of the composite endpoint of death, dialysis, or transplant ( $p=0.002$ ). In addition, compared with usual care, ferric citrate treated subjects had significantly fewer annualized hospitalization admissions and fewer days in the hospital. [Block, 2019, Figure 4].

**Figure 4.** Kaplan-Meier survival function curve for time to first hospitalization (A) and time to the composite end point of death, dialysis, or transplant in all patients (B).

### 5.3 Justification for Dose

The prescribed dose of study drug will be a fixed dose of 2 tablets orally taken with meals or snacks up to 3 times per day. The maximum daily dose is 6 tablets/day. This is the dose of ferric citrate that was utilized in the pilot randomized trial demonstrating clinical benefit on time to dialysis as described in Section 5.2, and has an established safety profile as it is the approved starting dose for the treatment of iron-deficiency anemia in patients with chronic kidney disease [Auryxia USPI 2021].

### 5.4 End of Study Definition

A participant is considered to have completed the study if he or she has completed all phases of the study including the last visit or the last scheduled procedure shown in the Schedule of Activities (SoA) (Section 1.3).

The end of the study will be considered complete after all randomized subjects have completed their final study visit (Month 9 or EOT) and 30-day safety follow-up visit.

Any subject who either receives a kidney transplant or initiates maintenance dialysis, and has not withdrawn consent from study participation, will have a vital status check performed at 30-days following the relevant event. The vital status check will ascertain the subject's mortality (alive vs. deceased).

### 5.5 Number of Study Sites

Up to 25 investigative sites in the US.

## 6.0 STUDY POPULATION

### 6.1 Inclusion Criteria

1. Adult patients  $\geq 18$  years old.

2. Diagnosis of NDD advanced CKD, regardless of etiology. Advanced CKD is defined as at least one local laboratory determined estimated glomerular filtration rate (eGFR)  $\leq 20$  ml/min/1.73m^2 (calculated per any commonly used method or equation for estimating eGFR) within 90 days of Day 1.
3. Most recent transferrin saturation (TSAT)  $\leq 45\%$  within 45 days of Day 1.
4. Most recent serum phosphate is  $\geq 3.0$  mg/dL within 45 days of Day 1.
5. Most recent ferritin  $\leq 500$  ng/mL within 45 days of Day 1.
6. Women of child-bearing potential must have a negative serum or urine pregnancy test within 30 days prior to Day 1 procedures. Can be performed on Day 1 if prior to any Day 1 procedures. Results must be available prior to the 1st dose of study drug.
7. Understands the procedures and requirements of the study and provides written informed consent and authorization for protected health information disclosure.

## 6.2 Exclusion Criteria

1. Patients who, in the opinion of the Investigator, have acute kidney injury rather than CKD.
2. Patients with planned/imminent maintenance dialysis, or that are anticipated to begin maintenance dialysis within 8 weeks from Screening, in the opinion of the Investigator.
3. A known allergy or intolerance to ferric citrate or any of its constituents.
4. Hypersensitivity reaction to previous oral iron therapy.
5. History of hemochromatosis or iron overload syndrome (e.g., hereditary sideroblastic anemia, thalassemia, polycythemia vera).
6. Active malignancy requiring current treatment except for non-melanoma skin cancer regardless of treatment.
7. Active drug or alcohol dependence or abuse (excluding tobacco use or use of medical or recreational marijuana) within the 12 months prior to Screening or evidence of such abuse, in the opinion of the Investigator.
8. Limited life expectancy ( $<6$  months) in the opinion of the Investigator.
9. Females who are known to be pregnant or are breast-feeding during Screening or are planning to become pregnant and breastfeeding during the study period.
10. Evidence of a clinically active infection requiring antibiotics at Randomization.
11. Unable to comply with study requirements or in the opinion of the Investigator, not clinically stable to participate in the study.
12. Use of an investigational medication or participation in an investigational study within 30 days prior to Day 1.
13. Patients with a scheduled date for receipt of living donor kidney transplant.

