F: Both height and weight will be collected at the Day 1 visit. Height may be self-reported. Weight only will be collected during the treatment period and may be captured using data from the clinical encounter.

G: Serum or urine pregnancy test (women of childbearing potential) must be done at any point within 30 days of Day 1. Can be performed on Day 1 if prior to any Day 1 procedures. Results must be available prior to the 1st dose of study drug.

H: Other laboratory assessments include urine chemistry, hepatic panel, magnesium, cystatin-C and PTH if available (section 9.4, Table 2).

I: The most recent laboratory assessments prior to EOT will be utilized

J: Routine concomitant medications will be assessed at each in-person visit (Screening, Day 1, Month 9). Concomitant medications of interest will be assessed at Screening at then at each subsequent study visit (see Section 9.5.1).

K: Targeted medical history (refer to section 9.2.1)

L: Collection begins at initiation of study drug treatment (1st dose of study drug) and continues through the follow-up visit. Refer to Section 9.5.2.

M: Prescription for study drug must be sent to USRC Rx Pharmacy for processing at time of randomization to ensure on-time delivery prior to Day 1. Refill prescriptions or changes to prescription will be sent to the pharmacy as needed. Dispensing will be a minimum of 3 months supply.

N: Collection begins at initiation of study drug treatment (1st dose of study drug) and continues through the follow-up visit. Refer to Section 9.5.2.

O: Endpoint assessment includes initiation of dialysis, vital status (alive or deceased), transplant, and hospitalization. Any subject who either receives a kidney transplant or initiates maintenance dialysis, and has not withdrawn consent from study participation, will have a vital status check performed at 30-days following the relevant event.

P: If there are delays related to shipment from the USRC Rx pharmacy, study drug will be provided to subjects within 12 days of the Day 1 visit.

Q: Study drug accountability is performed at in-person visits only.

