## **9.0 STUDY ASSESSMENTS AND PROCEDURES**

### **9.1 General Study Periods**

#### **9.1.1 Screening, Enrollment, and/or Randomization**

Written informed consent must be obtained prior to the subject entering the study and before protocol-directed procedures are performed. Study visits are intended to coincide with the standard of care (SOC) nephrology visit. Initial informed consent discussion, in most cases, will occur at a SOC visit.

- The *Screening period* will be a maximum of 45 days in duration. It is defined as the period of 45 days prior to Day 1 (Baseline). Local laboratory assessments used for eligibility must be within 45 days prior to Day 1, with the exception of eGFR which must be within 90 days of Day 1

If found eligible (and informed consent has been obtained), the subject will be randomized. Dosing will begin on Day 1.

The Screening laboratory values will be defined as the most recent local laboratory assessments obtained prior to Day 1 (within 45 days) with the exception of eGFR which must be within 90 days of Day 1.

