#### **Phosphorus and Iron Indices**

**Collection and evaluation of phosphorus and iron indices (TSAT and ferritin) must be performed and reviewed at an interval no less than quarterly. Failure to monitor these parameters is considered an important protocol deviation.**

In all instances in which phosphorus and iron indices are collected, the Investigator must independently review these results to assess clinical significance and determine whether study drug dose changes or temporary discontinuation are required. Timely review of the laboratory assessments by the Investigator or designee is anticipated. Appropriate documentation of clinical

significance and any resulting dose adjustments will be documented in the subject source documentation and eCRF.

In the event the Investigator determines that a specific quarterly assessment of phosphorus and iron indices (TSAT and ferritin) is outside SOC, a study-specific lab kit will be provided by the sponsor and used to collect blood for assessment of TSAT, ferritin, and phosphorus by a central laboratory. Central laboratory details are provided in a laboratory information sheet.

Blood or urine will be collected for the following laboratory evaluations listed below and will be conducted during the course of the study. For details regarding the timing of these assessments refer to Section 1.3.

- Pregnancy Test: A serum or urine pregnancy test will be performed according to the SoA (Section 1.3) for females of childbearing potential. These results must be available and must be negative before the subject takes the first dose of study drug. Additional serum or urine pregnancy tests may be conducted throughout the study at the discretion of the Investigator to establish the absence of pregnancy during the study.

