### **9.6.8 Reporting of Pregnancy**

A pregnancy in a female subject must be confirmed by a positive serum or urine test ( $\beta$ -human chorionic gonadotropin).

Female subjects should interrupt study drug if they think they are pregnant. The study drug should be immediately discontinued once the pregnancy of a female study subject has been confirmed. The study drug can be resumed once a negative pregnancy test is confirmed.

If any study subject becomes or is found to be pregnant while receiving study drug or within 30 days of discontinuing the study drug, the pregnancy must be recorded on the study-specific paper Pregnancy Reporting Form within 24 hours of awareness of the pregnancy.

The study-specific paper Pregnancy Reporting Form must be completed with all known information regarding the pregnancy at the time of reporting. Investigative site personnel will update the form with additional information regarding the pregnancy and the outcome of the pregnancy as it becomes available until the outcome of the pregnancy is reported.

The Investigator will follow the subject until completion of the pregnancy. Pregnancy in and of itself is not considered an AE; however, unexpected complications are considered AEs.

Additional information about pregnancy outcomes follows:

- Note that "spontaneous abortion" includes miscarriage and missed abortion.
- All neonatal deaths that occur within 1 month of birth should be reported, without regard to causality, as SAEs. In addition, any infant death after 1 month that the Investigator assesses as related or unrelated to the in-utero exposure to the study drug should also be reported.
- In the case of a live birth, the "normality" of the newborn can be assessed at time of birth.

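### Read literally, the planning limb of exclusion 9 requires plans for both pregnancy and breastfeeding, so it misses a woman who plans only to conceive while on study drug

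*Protocol*

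**What the plan says.** Protocol 6.2, criterion 9, excludes "Females who are known to be pregnant or are breast-feeding during Screening or are planning to become pregnant and breastfeeding during the study period". It has three limbs: known pregnancy, breast-feeding at Screening, and a plan for the study period. The limbs are separated by 'or'. Inside the third limb the two plans are joined by 'and'. The synopsis, in the text supplied, lists only inclusion criteria, so Section 6.2 is the only place where this rule stands.

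The other provisions on pregnancy are:

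- Protocol 6.1, criterion 6: "Women of child-bearing potential must have a negative serum or urine pregnancy test within 30 days prior to Day 1 procedures".
- Protocol 9.4, on the pregnancy test: "These results must be available and must be negative before the subject takes the first dose of study drug". Later testing is optional: "Additional serum or urine pregnancy tests may be conducted throughout the study at the discretion of the Investigator".
- Protocol 9.6.8: "Female subjects should interrupt study drug if they think they are pregnant". Drug stops at once when pregnancy is confirmed, and the pregnancy is followed to its end.
- Protocol 8.1.2 lists pregnancy among the reasons for which an Investigator may stop study drug or withdraw the subject.
- Protocol 6.2, criterion 11, lets the Investigator exclude someone who cannot comply or is not clinically stable. It does not mention pregnancy.

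Neither the protocol nor the SAP text supplied contains a contraception requirement.

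**The concern.** An eligibility criterion has to sort people correctly as it is worded. The rest of the protocol makes the intent clear: no one should start drug while pregnant, and drug stops if pregnancy occurs. A woman who intends to conceive during treatment is the obvious target of a planning limb. A limb that needs both plans does not reach her.

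Two things are at stake, both modest. One is safety: a woman who expects to become pregnant could be enrolled within the rules and exposed to drug until pregnancy is suspected. The other is consistency. Protocol 11.10.2 makes entry without meeting the criteria a notifiable deviation, and SAP 3.4.3 counts it as an important one. Enrolling this woman is a deviation if 'and' is read as 'or', and is not one if it is read as written.

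**Working it through.** **Step 1: what the words can mean.** The planning limb allows three readings.

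1. She plans to become pregnant and plans to breastfeed, both within the study period. Both plans are needed.
2. She plans to become pregnant and is also breastfeeding. Both conditions are needed again. A woman already breastfeeding at Screening is excluded by the second limb in any case, so this adds almost nothing.
3. The limb covers two groups: women planning pregnancy, and women planning to breastfeed. Either plan excludes. This is almost certainly what was meant, but it requires reading 'and' as 'or'.

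**Step 2: how much readings 1 and 3 differ.** Inputs from the documents: treatment lasts 270 days (Protocol 9.1.2), the study ends at Day 300 (Schedule of Activities), and the SAP caps the follow-up visit at Day 307 (SAP 3.3). The documents give no length of pregnancy. I assume 280 days, and show 260 days to test sensitivity.

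Latest day of conception that still allows birth in the period = last day of the period − length of pregnancy.

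| Period ends on | 280 days assumed | 260 days assumed |
|---|---|---|
| Day 270 (end of treatment) | 270 − 280 = −10: none | 270 − 260 = Day 10 |
| Day 300 (end of study) | 300 − 280 = Day 20 | 300 − 260 = Day 40 |
| Day 307 (SAP cap) | 307 − 280 = Day 27 | 307 − 260 = Day 47 |

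With 280 days and Day 300, a plan to conceive on any of the last 270 − 20 = 250 of the 270 treatment days falls outside reading 1. In the most generous cell it is 270 − 47 = 223 of 270. Even a woman who plans to conceive earlier is caught only if she also plans to breastfeed before the study ends. Reading 1 is therefore close to empty, whichever cell is used.

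**Step 3: whether anything else excludes her.**

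| Provision | Reaches a woman who plans only to conceive? |
|---|---|
| Inclusion 6 (6.1) | No. It tests for current pregnancy, not intent. |
| Exclusion 9, first two limbs | No. They cover known pregnancy and breast-feeding at Screening. |
| Exclusion 11 (6.2) | Only if the Investigator chooses to apply a general rule. |
| 8.1.2 and 9.6.8 | No. They act after pregnancy is suspected or occurs. |
| Contraception rule | None in the text supplied. |

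**Step 4: effect on the results.** The wording enters no sample-size input, endpoint definition or model term. The number of women of child-bearing potential is not given, so the number affected cannot be estimated.

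**The case against.** The best reply is that the literal reading is too odd for anyone to adopt. Because almost no woman could plan both events in about ten months, a sensible reader takes either plan as excluding, and most sites probably do. On that view, two sites classifying the same woman differently is speculation. This stands in part: it is why the practical effect is small. But it concedes that the sentence works only when it is not read as written, which is a reason to correct it.

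A second reply is that exclusion 11 already lets an Investigator turn the woman away, since she intends a state in which drug must be stopped. It can be used that way. However, it is discretionary, does not name pregnancy, and gives no uniform rule across up to 25 sites.

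A third is that consent pages were removed from the copy reviewed and may contain counselling on pregnancy or contraception. That cannot be ruled out. Such counselling would still not alter the eligibility text.

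A fourth is that the documents state a pregnancy risk only for iron overdose (Protocol 9.7), not for the trial dose. That is correct, and it limits how serious the gap is.

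**Conclusion.** The point holds as a minor, safety-relevant wording error in one criterion. As written, the planning limb excludes almost no one and misses a woman who plans only to conceive on drug. This rests on the literal reading, on an assumed pregnancy of 260 to 280 days, and on the absence of a contraception rule from the text supplied. There is no effect on power or the primary analysis.

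A reader might infer more: that pregnancy testing also fails when shipment is late. Protocol 9.1.1 says "Dosing will begin on Day 1", yet Schedule of Activities footnote P allows that "study drug will be provided to subjects within 12 days of the Day 1 visit". A test 30 days before Day 1 would then be 30 + 12 = 42 days old at first dose. The documents do not make this an error:

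- The window runs from Day 1, not from first dose. Footnote G says the test "must be done at any point within 30 days of Day 1", and inclusion 6 agrees.
- Section 9.4 requires a negative result before dosing but sets no maximum age for it. A delay breaches no stated limit.
- The 42 days need the earliest permitted test and the full delay. A test at the start of the Randomization window gives at most 8 + 12 = 20 days. A test 18 days or less before Day 1 never exceeds 18 + 12 = 30.
- The protocol schedules no pregnancy test during 270 days of dosing. Trimming at most 12 days beforehand would gain little.

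A 30-day limit at first dose would be a preference, and no repeat test is proposed.

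Nor should a reader infer that known pregnancy is admitted or left unmanaged. Exclusion 9's first limb, inclusion 6 and Section 9.6.8 deal with it.

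**What to change.** Reword the last limb of exclusion 9 in Protocol 6.2 to: *or are planning to become pregnant or to breastfeed during the study period*. Leave inclusion 6, Schedule of Activities footnotes G and P, and Section 7.1.2 as they are.

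This is one edit in one place. Protocol amendments need prospective IRB/IEC approval (Protocol 11.2) and there may be up to 25 sites (Protocol 5.5), so it should go into the next amendment rather than prompt its own. The expected cost in recruitment is at most a few extra screen failures. Because most sites probably apply the rule this way already, there may be none.
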